[USE THIS BIOMEDICAL PROTOCOL TEMPLATE IF YOUR PROJECT INVOLVES ANY PHYSICAL CONTACT OR MEDICAL INTERVENTIONS WITH PARTICIPANTS]

INSTRUCTIONS:

- Depending on the nature of your research, some sections may not be applicable to your research. These sections can be removed as needed.
- When you write a protocol, keep an electronic copy. You will need to modify this copy when making changes.

PROTOCOL TITLE:

Treatment of Stress-Related Psychopathology: Targeting Maladaptive and Adaptive Event Processing

PRINCIPAL INVESTIGATOR:

*[name]
Psychological Sciences
[contact]
[contact]*

UH FACULTY ADVISOR:

If the principal investigator's primary role at UH is resident, fellow or student, identify a faculty advisor.

N/A

OTHER DEPARTMENTS INVOLVED IN THIS STUDY (IF APPLICABLE):

N/A

VERSION NUMBER:

Include the version number of this protocol if assigned by an outside entity.

N/A

DATE:

12/14/2021

Objectives

Directions: Describe the purpose, specific aims or objectives. Be sure to also include the hypothesis being tested

Positive Processes and Transition to Health (PATH) includes six, 90-min sessions that target maladaptive event processing (unproductive processing, avoidance, and impaired reward sensitivity), while also promoting parallel adaptive event processing (constructive processing, approach, and reward seeking) for destabilizing life events and for positive events. PATH uses a platform of narrative revisiting of destabilizing life events, as well as positive life event reminiscence. Patients will be selected for having experienced a destabilizing life stressor and related psychopathology. The R61 trial ($N = 45$) will examine whether PATH engages the therapeutic targets, with clear Go/No Go rules. In the R33, patients ($N = 135$) will be randomized to PATH or progressive muscle relaxation (PMR) and assessed over a 3-month follow-up.

The Specific Aims are:

Specific Aim 1: Engage Therapeutic Targets (R61): In an open trial ($N = 45$), we will examine whether PATH changes therapeutic targets (unproductive processing, avoidance, impaired reward processing) from pre- to 3-month follow-up, with at least medium effects ($d = 0.60$) on two of three primary target measures and at least ($d = 0.50$) on one secondary target measure. We will examine dosing and timing of effects.

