Potentially eligible individuals will complete their informed consent in-person before starting intake (see below for COVID-19 changes). Participants will be informed that participation is optional and that they may discontinue participation at any time. Participants will be provided with the contact information for study staff and the Human Subjects division.

COVID-19 CHANGES

Potentially eligible individuals will complete their informed consent via REDCap, while an assessor is on Zoom with them. Assessors will provide participants with the same information as above. Consent forms have been uploaded that reflect changes to an online and remote intervention and assessments. Assessors will also ask about collecting emergency contact information, in case it's ever needed.

Sharing of Results with Research Participants

Directions: Describe whether results (study results or individual subject results such as results of investigational diagnostic tests, genetic tests, or incidental findings) will be shared with the research participants or others (e.g. the subject's primary care physicians) and if so, describe how the results will be shared.

- Results will not be shared with research participants
- Results will not be shared with research participants' doctors

Study Design

Directions: Describe and explain the overall study design. (eg: single visit, single-blind, double-blind, non-randomized, randomized, blood draw, investigational drug, device etc.)

[figure not shown]
Open Trial of PATH: Engage the Targets (R61)

The R61 will be an open trial to determine if Positive Processes and Transition to Health (PATH) engages the proposed targets: unproductive processing, avoidance, and reward deficits in a *sample of 45 adults* who have experienced a destabilizing life event involving profound loss or threat, report persistent stressor-related symptoms of PTSD and/or depression, and are elevated on symptoms related to 2 of the 3 therapeutic targets. Patients will receive six 90 minute sessions of PATH (with 2 boosters, if partial responders). Primary targets will be assessed at pre-treatment, week 3, post-treatment, and at 1- and 3-month follow-up; secondary targets at pre-treatment, weekly during treatment, post-treatment, and at 1- and 3-month follow-ups. If GO criteria are achieved (Table 3), we will proceed to the R33.

RCT of PATH: Target Engagement and Link to Clinical Outcomes (R33)

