Treatment dropout, defined as completing fewer than 4 sessions. Homework adherence between sessions will be assessed using a modified version of the Utility of Techniques Inventory (UTI, Foa et al., 1999). As is standard in many cognitive and behavioral treatment approaches, therapists will also complete an in-session record of client engagement/adherence; specifically, therapists will complete the Negative Event Revisiting Recording Form, on which they record clients' subjective units of distress (SUDs) every 5 minutes while clients engage in the negative event revisiting exercise during sessions 2 through 6. Similarly, therapists will complete the Positive Event Reminiscence Recording Form, on which they record clients' subjective units of pleasure (SUPs) every 5 minutes while clients engage in the negative event revisiting exercise during sessions 2 through 6. Treatment credibility (Treatment Credibility Scale, CS, Addis & Carpenter, 1999) and client satisfaction (Client Satisfaction Questionnaire, CSQ-8; Attkisson & Greenfield, 1994; 2004) will also be assessed. Finally, therapist adherence will be rated via independent rater using a to-be-developed checklist based on a random subset of 10% session recordings.

Milestones (Go/No Go Criteria)

Go/No Go Criteria. For "Go" to be achieved and to proceed to the R33, two criteria must be met. See Table 3. The first is that at least 2 of the 3 primary targets must change. A moderate effect size ($d = 0.60$) was chosen to reflect evidence of clinically meaningful target engagement (see Gold et al., 2017), in line with NIMH guidelines for a preliminary signal of target engagement/efficacy in intervention trials.

Table 3. Target Mechanism Engagement

Phase	Target Mechanism/Outcome	Primary Indicator	Secondary (self-report) Indicator	Go/No Go ¹ Pre-Post Effect Size (Cohen's d)
R61	Unproductive Processing	Affective Updating Task		$d \geq 0.60$
			Posttraumatic Cognitions Inventory	$d \geq 0.50$
	Avoidance	Idiographic Behavioral Approach Task		$d \geq 0.60$
			Behavioral Activation for Depression Scale	$d \geq 0.50$
	Reward Deficit	Probabilistic Reward Task		$d \geq 0.60$
			Snaith-Hamilton Pleasure Scale	$d \geq 0.50$
R33	Posttraumatic Stress Severity	PTSD Symptom Scale-Interview		$d \geq 0.80$
	Depression Severity	Quick Inventory of Depressive Symptomatology-Interview		$d \geq 0.80$

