Note. ¹For Go to R33, at least 2 of the 3 primary mechanism indicators must change and at least one of the secondary indicators must change. For

Second, at least one of the secondary measures must show a moderate effect ($d = 0.50$) from pre- to post-treatment. We included measures of each of the targets, as they are conceptualized as interrelated parts of a "stuck" system. For "Go" to an R01 after the R33, in addition to target engagement, primary outcomes of PTSD and depression must show clinically meaningful gains (e.g., Barth et al., 2016; Cusak et al., 2016).

R33 PATH Refinement. Beyond examining outcome data from the R61, we will: 1) conduct interviews with standardized questions with 20% of patients, selecting those with small and large gains on therapeutic targets; 2) conduct a feedback session with therapists to identify aspects of the manual that need refinement; and 3) examine booster session data regarding whether additional sessions are needed for the R33. The interview guides will be submitted as through a modification before they are conducted.

Data Analysis Plan

Directions: Describe the data analysis plan, including any statistical procedures. If applicable, provide a power analysis, describe primary and secondary study endpoints including safety endpoints.

General Analytic Strategy

For Specific Aims 1–3, we will use random effects models, a specific application of general linear mixed models (GLMMs) that helps to address common issues with longitudinal clinical treatment data, including missingness, serial correlation, and time-varying covariates (e.g., Gallop & Tasca, 2009). These models allow for person-specific deviations from overall mean time effects and are robust to missing data, using maximum likelihood estimation in cases of ignorable non-response. This analytic approach allows for initial modeling of different covariance structures, as well as non-linear time transformations that are especially useful when between-assessment intervals are not consistent across time. For Aim 3, mediation will be tested using the product of coefficients method with bootstrapped standard errors (MacKinnon, 2009) and based on a lagged mediation design (e.g., Hofmann, 2006). This approach addresses the need for temporal precedence of predictor to outcome and accounts for change between time points of a target DV. Analyses involving secondary metrics (i.e., PTCI, BADS, SHAPS) will shift to a more conservative GLM framework.

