Our approach to power analyses aims to balance pragmatic factors with analytic considerations. We focus primarily on Specific Aim 1 (R61) and Specific Aim 2 (R33). Primary analyses for both aims will involve random effects models; however, because it is difficult to accurately estimate covariance structures of such models, *a priori* power or sample size estimations have limited value. Fang (2006) has shown that ideal sample sizes often far exceed clinical resources for conventional trials, whereas other studies have shown that small sample sizes do not bias estimates of fixed effects (e.g., Bell et al., 2008). Accordingly, we frame our power calculations in line with GLM models that mirror the primary tests and hypotheses of our more complex random effects/GLMM models. In general, estimates were calculated based on $\alpha = .05$ and power $(1 - \beta) = .80$, using intent-to-treat, repeated-measures designs (e.g., paired t-tests). Power calculations were completed using G*Power (Faul et al., 2007). For Aim 1, with an estimated pre-post effect size of $d = 0.60$ (one-tailed tests), we are well-powered with a sample of 45. In fact, for a sample size of 45, an alpha of .05, and power of .80, we will be able to detect a small to moderate effect size of .38. For Aim 2, we based power estimates on a primary comparison of time by treatment interaction in an RMANOVA model. For a five time points, two groups, RMANOVA with a correlation of $r = .70$

between measures, we are well powered to detect treatment X time small effect size of .07 with 67 patients per treatment. For Specific Aim 3, using Monte Carlo simulations in MPlus 6.0 (Muthen & Muthen, 2002) with the same alpha, power, and sample size of at least 67 per condition, we are adequately powered to detect an indirect effect size as small as $d = .50$.

Specific Aim 1: Engage Targets (R61)

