We will examine whether PATH engages targets with at least medium-size effects ($d = 0.60$) on 2 of 3 of primary targets from pre- to post-intervention. Primary target dependent variables are: Affective Updating, BAT, and PRT. We will conduct a planned contrast of pre- and follow-up time points within each separate model. This test is analogous to a contrast in ANOVA or a paired t-test, but superior in terms of estimation of missing data and modeling of covariates. The resulting test yields an effect size that can be converted to a d (Feingold, 2013) and compared to our target threshold of $d = 0.60$ for all three models as part of our Go/No-Go rules. For secondary measures of PTCI, BADS, and SHAPS, we will use the GLM approach described above and compare to our target threshold of $d = 0.50$ as part of our Go/No-Go rules.

Dosing and timing of treatment effects. Dosing will be assessed by graphing individual symptom trajectories to identify groups of individuals who may need more treatment, including specifically the shift of positive and negative affect over time (PANAS). To understand timing of effects, primary analyses will be augmented with tests focused on brief, critical change intervals, yoked to the introduction of new target-related content (session k). We will compare residualized change in target (primary measures: Affective Updating, BATs, PRT) in the pre-introduction phase (session k-1 to session k) to change in the post introduction phase (session k+1 to session k+2). These windows will differ for each target, as they are introduced sequentially (e.g., reward deficits, pre-introduction = session 1 and 2, post-introduction = session 3 and 4). Change scores will be compared using t-tests. Similar analyses will be utilized with the PANAS.

Specific Aim 2: Replication of Target Engagement (R33)

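### The R61 Go/No-Go thresholds are set on pre-to-post change in Table 3, but Specific Aim 1 and the contrast that yields the primary decision statistic run from pre-treatment to follow-up

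*Combined protocol and SAP*

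**What the plan says.** Study Design makes the R33 conditional on the R61 milestones: "If GO criteria are achieved (Table 3), we will proceed to the R33". The places that state or feed the rule do not agree on the interval.

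**Pre to post**
- Table 3, threshold column heading: "Pre-Post Effect Size".
- Milestones (Go/No Go Criteria), second criterion: "at least one of the secondary measures must show a moderate effect ($d = 0.50$) from pre- to post-treatment".
- Power Analysis, Aim 1: "with an estimated pre-post effect size of $d = 0.60$ (one-tailed tests".
- Data Analysis Plan, Specific Aim 1, first sentence: the 0.60 effect is sought "on 2 of 3 of primary targets from pre- to post-intervention".

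**Pre to follow-up**
- Objectives, Specific Aim 1: "we will examine whether PATH changes therapeutic targets (unproductive processing, avoidance, impaired reward processing) from pre- to 3-month follow-up". Both the 0.60 and the 0.50 thresholds hang on this sentence.
- Data Analysis Plan, Specific Aim 1, two sentences after the pre-to-post wording: "We will conduct a planned contrast of pre- and follow-up time points within each separate model". The effect size from this contrast is then "compared to our target threshold of $d = 0.60$ for all three models as part of our Go/No-Go rules".

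**No visit named**
- The Milestones prose for the primary criterion.
- The sentence on secondary measures in the Specific Aim 1 analysis.

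**The concern.** A Go rule should produce one number per measure from one named visit, fixed in advance. Here the table that defines the rule asks for one contrast and the analysis text prescribes another. A statistician who follows the planned contrast computes a different quantity from the one Table 3 asks for. One who follows the opening sentence of the same paragraph does not.

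The two quantities also differ in meaning. A pre-to-post contrast measures response to the six sessions. A pre-to-follow-up contrast measures later status, after two booster sessions for some patients and whatever fading or further treatment has occurred. If the visit stays open, it can be settled after both results are known. What hangs on it is whether a 135-patient randomised phase starts.

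**Working it through.** **1. The passages side by side**

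| Place | Interval | Threshold |
|---|---|---|
| Objectives, Specific Aim 1 | pre to 3-month follow-up | 0.60 and 0.50 |
| Table 3 | pre to post | 0.60 and 0.50 |
| Milestones, first criterion (prose) | none named | 0.60 |
| Milestones, second criterion | pre to post | 0.50 |
| Power Analysis, Aim 1 | pre to post | 0.60 |
| Specific Aim 1 analysis, first sentence | pre to post | 0.60 |
| Specific Aim 1 analysis, planned contrast | pre to follow-up, 1 or 3 months not stated | 0.60 |
| Specific Aim 1 analysis, secondary measures | none named | 0.50 |

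Follow-up is not a loose synonym for post. Study Design lists pre-treatment, week 3, post-treatment, 1 month and 3 months as separate assessments of the primary targets. The Specific Aim 3 analysis treats change to post-treatment and change to follow-up as two intervals. Study Procedures describes the boosters after the post-treatment assessment and before the follow-ups.

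**2. The plan's own figure**

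Inputs from Power Analysis: N = 45, one-tailed α = .05, power .80, paired t-test. Power is 1 − F(t₀.₉₅,₄₄), where F is the noncentral t distribution with 44 df and noncentrality d√45.

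- Detectable d at 80% power: 0.376, against .38 stated.
- Power at d = .38: 80.6%. Power at d = 0.60: 99.0%.
- Normal check: (1.645 + 0.842)/√45 = 2.487/6.708 = 0.371.

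The stated figure reproduces, and it does not depend on which visit is chosen.

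**3. How sharply the rule turns around 0.60**

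Assumptions: d on the SD of change, three independent tasks with equal true d, and Go judged on the point estimate. For one task, p = P(observed d ≥ 0.60) = 1 − F(0.60√45), with noncentrality d√45. For two of three, P = 3p²(1 − p) + p³.

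| True d | p, one task | P, at least 2 of 3 |
|---|---|---|
| 0.40 | 0.113 | 0.035 |
| 0.50 | 0.276 | 0.186 |
| 0.60 | 0.509 | 0.513 |
| 0.70 | 0.738 | 0.830 |
| 0.80 | 0.895 | 0.969 |

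Example at 0.60: 3 × 0.509² × 0.491 + 0.509³ = 0.382 + 0.132 = 0.513. A shift of 0.1 to 0.2 in d between visits can therefore change the decision.

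**4. Both visits in the same trial**

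Simulation of 20,000 trials per cell: n = 45, three targets at three visits (pre, post, follow-up), multivariate normal, unit SD. The documents give no R61 visit correlation, no between-target correlation and no expected change between post and follow-up, so these were varied:
- visit correlation .50 or .70 (.70 is stated only for Aim 2);
- between-target correlation 0, .3 or .5;
- d on the pre-treatment SD or on the SD of change.

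That makes 12 cells per scenario. There are no missing data, and the secondary criterion is ignored.

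| True d, post / follow-up | Trials in which the two visits give opposite answers |
|---|---|
| 0.40 / 0.40 | 2.3–11.7% |
| 0.50 / 0.50 | 17.1–27.2% |
| 0.60 / 0.60 | 31.4–38.3% |
| 0.70 / 0.70 | 15.6–26.0% |
| 0.80 / 0.80 | 2.0–10.7% |
| 0.70 / 0.50 | 55.8–74.9% |
| 0.80 / 0.70 | 12–22% |
| 0.90 / 0.80 | 1–7% |

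In the 0.70 / 0.50 case, P(Go) is 0.775–0.884 at post and 0.139–0.240 at follow-up. Repeating the simulation moved the limits by about one percentage point at most.

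**The case against.** The conflict itself is hard to dispute. Its weight can be contested on four grounds.

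- **Table 3 governs.** Study Design points to it, the second criterion agrees with it, and the Aim 1 analysis opens in line with it. On that reading the rule is usable, with two sentences out of step. This is a fair account of the default. But one of those two sentences is the only primary contrast the plan specifies, and the other is the stated aim.
- **The table heading may be loose.** The same column holds the R33 symptom rows, while Specific Aim 3 in the Objectives measures symptom improvement to 3 months. Pre-post there could simply mean within-person change. If so, the intended visit is less clear, which strengthens the case for naming it.
- **The simulation is illustrative.** The 31–38% at equal true effects is sampling noise at the cut-off, not a shift caused by the visit. The 56–75% depends on an assumed fade that straddles 0.60; for 0.80 falling to 0.70 it is 12–22%. Boosters could also raise effects at follow-up. All of this stands, so the seriousness should rest on what the rule decides.
- **Booster timing is partly inferred.** The order follows from how Study Procedures and the data-collection section are laid out. The text does not say whether the 1 and 3 months run from session six or from the last booster. This also stands.

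**Conclusion.** The plan contradicts itself on the interval for the R61 Go decision, for the primary criterion and for the secondary one, and the planned contrast leaves the follow-up visit unnamed. Pre-to-post is the better-supported reading, but the documents do not settle it. This must be fixed because the rule gates the R33.

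The practical size depends on where the true effects lie. Under the assumptions above, the choice of visit matters most near 0.60, the value the plan itself uses for power, where the two visits disagree in about a third of trials. It matters little at 0.40 or 0.80 when the effect is the same at both visits. The sample size of 45 and the detectable effect of .38 are correct and are not in question.

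**What to change.** Before R61 data are examined, name one visit for both Go criteria. Use it in the Objectives, Table 3, the Milestones prose, Power Analysis and the Specific Aim 1 analysis, including its sentence on secondary measures. The choice is the team's.

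- **Post-treatment (smallest edit).** Change Specific Aim 1 in the Objectives and the planned contrast to pre- to post-treatment, in line with Table 3. Report the 3-month contrast as supportive only, unable to trigger Go. Downside: this reworks a stated aim, and Aim 2, titled a replication, is set at 3 months, so the R33 would replicate over a different interval from the Go rule. The supportive 3-month R61 estimate is the bridge.
- **3 months.** Change Table 3, the second criterion, the power statement and the first sentence of the Aim 1 analysis. Name the 3-month visit in the contrast and state the point from which the 3 months are counted. Downside: more text changes, and the Go decision waits for the last 3-month visit.

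Either way the edit is to wording only, with no new patients, visits or data, though it does fix what the Go rule measures.

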Specific Aim 2: Replication of Target Engagement (R33): In a randomized control trial ($N = 135$), we will examine whether PATH alters therapeutic targets from pre- to 3-month follow-up in comparison to PMR.

Specific Aim 3: Link Changes in Targets to Changes in Stressor-related Outcomes (R33): We will examine whether changes in therapeutic targets (pre- to post-) predict improvement in PTSD and depression symptoms (pre- to 3-month follow-up).

Specific Aim 4: Feasibility and Dropout/Acceptability of PATH (R61/R33): We will examine whether patients perceive PATH as helpful and complete/adhere to treatment, and therapist fidelity.

There is an urgent need to develop novel treatments, given the prevalence, impact, and cost of PTSD and MDD (e.g., Hoge & Chard, 2018). PATH is an innovative intervention that targets three interrelated, transdiagnostic processes that maintain stressor-related psychopathology. PATH's unique early and sustained focus on positive emotions could improve adherence and outcome, particularly in those with the reward deficits commonly seen in PTSD and MDD. Further, PATH's focus on positive emotions and "stuck" processing targets unique processes largely absent in current PTSD therapeutics. PATH is novel in applying exposure principles to depression, not just PTSD. This brief, positive, mechanistically precise, transdiagnostic treatment has the potential to improve treatment engagement and outcomes, identify clear therapeutic targets that predict better outcomes, and ultimately reduce the costly burden of stressor-related psychopathology.

We hypothesize that (1) those in PATH will have significant changes in the therapeutic targets, (2) those in PATH will show a greater change in therapeutic targets than those receiving Progressive Muscle Relaxation (PMR), (3) changes in therapeutic targets predict improvement in PTSD and depression symptoms, and (4) those in PATH will perceive the intervention as helpful and adhere to treatment.

Background

Directions: Describe the relevant prior experience and gaps in current knowledge describing how it will add to existing knowledge. Include any relevant preliminary data.

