Refine PATH					X							
Procedures Finalized and Staff Trained					X							
Final IRB Approval and Material Prep					X							
Assessor and Therapist Training	X				X			X				X
Recruit Participants		X	X	X	X	X	X	X	X			X

Patient Treatment	X	X	X	X	X	X	X	X	X	X
Assessment	X	X	X	X	X	X	X	X	X	X
25% Recruitment Target (n = 34)			X							
50% Recruitment Target (n = 67)					X					
75% Recruitment Target (n = 101)							X			
100% Recruitment Target (n = 135)								X		
Analyzing and Interpreting Results									X	X
Manuscript Preparation and Submission									X	X
General Grant Procedures									X	X
Research Performance Progress Reports			X			X		X		X
Data Sharing NDCT	X		X		X		X		X	X

Phone Screening. Members of the study team will collect demographic data and complete an eligibility screening form (type of destabilizing event, inclusion/exclusion criteria). Brief versions of the PSS-I and QIDS-C will be used. Potentially eligible individuals will be scheduled for an intake; those excluded will be given referrals and we will retain their demographic information and reason for exclusion for the creation of consort diagrams. All clinical data will not be utilized and ultimately deleted.

Pre-treatment Assessment. After informed consent, a study team member (licensed therapist or under the supervision of someone licensed) will administer measures of PTSD (PSS-I), depression (QIDS-C), and suicidality (C-SSRS). Assessors will be blind to treatment assignment (in R33). Patients will complete baseline self-reports and laboratory paradigms. See Figure 2.

Active Treatment. Someone on the study team (licensed or under the supervision of someone licensed) will administer the treatment sessions. In the R61, all patients will receive PATH. In the R33, patients will be randomized to PATH or PMR, using a computerized algorithm accounting for initial symptom severity.

Post-Treatment Assessment. A study team member, either someone licensed or under the supervision of a licensed therapist, will re-administer PSS-I, QIDS-C, and C-SSRS; patients will complete self-reports and tasks of target engagement. Treatment dropouts will be immediately assessed and will stay in the assessment portion of the study.

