Data will be screened for accuracy, missing values, and fit with the assumptions of GLMM (e.g., linearity, multivariate normality; Tabachnick & Fidell, 2007). Data transformations or model re-specifications will be performed, if needed. Outcome data will be plotted against time to guide selection of applicable time variables; similarly, covariance matrices will be examined to inform selection of the best covariance structure. Best fitting models will be evaluated based on these plots and model fit information (e.g., AIC, BIC). We will use pattern-mixture models to examine whether missingness can be considered ignorable. For non-ignorable missing data, values will be multiply imputed and data recombined (Rubin, 1987) in the mixed model program or comparable model-supported approaches. We will examine associations between primary dependent variables with factors such as gender and time since event and make appropriate adjustments (e.g., covarying predictors). In analyses nesting subjects within treatments (Aim 2), dummy codes will be used (Snijders, 2005).

Power Analysis

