We will examine whether PATH alters therapeutic targets in comparison to PMR. Primary dependent variables are Affective Updating, BATs, PRT. Secondary dependent variables are PTCI, BADS, and SHAPS. We will compare the main effect of treatment (PATH or PMR) over time separately in each of three models. These models will estimate the effects of treatment on both the level of the target at 3-month follow-up and change over time (slope). Random intercepts and random coefficients for time-varying covariates (e.g., time) will be specified, if the model fit is better than a fixed effects model. For example, $y_{ik} = \beta_0 + \beta_1 \text{Time}_{ik} + \beta_2 \text{Treatment}_{ik} + \beta_3 (\text{Treatment}_{ik} \times \text{Time}_{ik}) + v_{0i} + v_{1i} \text{Time}_{ik} + \epsilon_{ik}$ where Treatment represents a dummy-coded effect (Group = 0 for PATH, 1 for PMR), i=subject, k=time, and y = DV of interest. We hypothesize that differences will emerge between PATH and PMR specifically for Affect Updating, BAT, and PRT. For secondary measures, we will use the GLM approach above in an ANCOVA-like design to test the interaction of treatment and time.

Specific Aim 3: Linking Changes in Targets to Changes in Stressor-related Symptoms (R33):

We will examine whether changes in target mechanisms (pre- to post-) predict improvement in PTSD (PSS-I) and depression (QIDS-C) at pre-, mid, post-, 1-, 3-month follow-up. In GLMs, we will evaluate targets from pre- to post-treatment and at 3-month follow-up, with corresponding metrics to assess change in symptoms (PSS-I, QIDS-C). In the GLMs, treatment will predict changes in symptoms from pre- to post-treatment (controlling for baseline levels) and pre- to follow-up. GLMMs will be conducted as above, and treatment will be used to predict levels and change in symptoms. Next, in GLMs, we will

predict pre-post change in target mediators (unproductive processing, avoidance, reward deficits) from treatment (A path) and follow-up outcomes from the mediator (B path), controlling for treatment and baseline symptoms. GLMM will test for mediation by predicting the mediator at all time points from treatment, and the outcome at all time points from the mediator, controlling for treatment. Similar analyses will be used for secondary measures.

Specific Aim 4: Feasibility and Dropout/Acceptability of PATH Intervention (R61/R33):

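### The Aim 2 example model for the primary targets leaves the arms free to differ at pre-treatment and omits the randomisation severity variable, which costs precision but not validity

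*Combined protocol and SAP*

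**What the plan says.** The Specific Aim 2 section covers Affective Updating, BAT and PRT in three separate mixed models. It announces: "We will compare the main effect of treatment (PATH or PMR) over time separately in each of three models". It continues: "These models will estimate the effects of treatment on both the level of the target at 3-month follow-up and change over time (slope"). The example equation contains an intercept, Time, Treatment, Treatment by Time, and a random intercept and slope. An ANCOVA-like design is mentioned there for the secondary measures only, and control for baseline levels appears under Aim 3 for the symptom models.

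Four other places bear on this.

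- Study Timeline, Active Treatment: patients are randomised "using a computerized algorithm accounting for initial symptom severity". The scale is not named.
- General Analytic Strategy: "We will examine associations between primary dependent variables with factors such as gender and time since event and make appropriate adjustments". The same section lets the covariance structure be chosen from the data and allows "non-linear time transformations that are especially useful when between-assessment intervals are not consistent across time".
- Power Analysis: "we based power estimates on a primary comparison of time by treatment interaction in an RMANOVA model". These calculations are described as "GLM models that mirror the primary tests and hypotheses of our more complex random effects/GLMM models".
- Objectives, second hypothesis: "those in PATH will show a greater change in therapeutic targets than those receiving Progressive Muscle Relaxation (PMR").

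**The concern.** Randomisation makes the arms equal in expectation at pre-treatment. A free treatment intercept spends information estimating a difference known to be zero on average, and this widens the standard error of the treatment contrasts. The pre-treatment task scores are collected anyway, so the gain from using them fully needs no further data.

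The severity variable that enters the allocation is absent from the example model, and nothing guarantees that it will be added. Selecting covariates by their observed association with the outcome leaves the treatment estimate open to selection.

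The Aim 2 section also lists level and slope side by side and speaks of a main effect. It does not repeat that the Power Analysis treats the interaction as primary, so a reader of that section alone cannot tell which result decides if the two differ.

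**Working it through.** **The plan's own figure.** For the repeated-measures interaction, λ = f²·N·m/(1 − r), with m = 5, r = .70, N = 134 and 4 and 4(N − 2) = 528 degrees of freedom. Power of 80% at .05 is reached at f = 0.0734, which agrees with the stated .07 to two decimals. The common correlation of .70 therefore describes the power design correctly and is used below.

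**Inputs.** From the documents: n = 67 per arm, r = .70, α = .05, power .80, five assessments (pre, week 3, post, 1 and 3 months). Assumed: two-sided tests, complete data, SD 1, no random slope, and assessment weeks t = 0, 3, 7, 11, 19 (T = 19). The documents give no pre to 3-month correlation for these tasks, so r = .50 is a sensitivity value.

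**Formulas.** Let V be the within-person covariance, A = 1′V⁻¹1, B = 1′V⁻¹t and D = t′V⁻¹t. For equal arms with linear time, the variances of the treatment contrasts are:

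- slope × T, free intercepts: (2/n)·T²/(D − B²/A)
- 3-month level, free intercepts: (2/n)·(D − 2TB + T²A)/(AD − B²)
- either contrast, common pre-treatment mean: (2/n)·T²/D

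With time coded 0 at pre-treatment and a common mean there, the slope over 19 weeks and the 3-month difference are the same parameter. The detectable difference is 2.822 × SE (noncentral t, 132 df), and 2/n = 0.02985.

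**Compound symmetry, r = .70.** Σt = 40 and Σt² = 540. A = 5/3.8 = 1.316; B = 40/3.8 = 10.526; D = (540 − (.7/3.8)·1600)/.3 = 817.5.

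- Free slope: D − B²/A = 733.3; variance 0.02985 × 361/733.3 = 0.0147.
- Free level: (817.5 − 400 + 475)/964.9 = 0.925; variance 0.0276.
- Common mean: 0.02985 × 361/817.5 = 0.0132.

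**Compound symmetry, r = .50.** A = 1.667, B = 13.333, D = 546.7. The variances are 0.0245 (slope), 0.0261 (level) and 0.0197 (common mean).

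**First-order autoregression by visit, .70.** A = 1 + 4(.09)/.51 = 1.706; B = .3 × 25.3/.51 = 14.88; D = (9 + 24.01 + 37.21 + 127.69)/.51 = 388.1. The variances are 0.0417, 0.0297 and 0.0278.

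| Covariance | Slope × T, free | Level, free | Common mean (both) | Variance ratio, slope | Variance ratio, level |
|---|---|---|---|---|---|
| Compound symmetry, .70 | 0.342 | 0.469 | 0.324 | 1.115 | 2.095 |
| Compound symmetry, .50 | 0.442 | 0.456 | 0.396 | 1.242 | 1.325 |
| Autoregressive, .70 | 0.577 | 0.486 | 0.470 | 1.50 | 1.07 |

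At the plan's r = .70 the slope gain equals the precision of 67 × 1.115 = 74.7 per arm.

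**Sensitivity.** Under compound symmetry, weeks 0, 3, 6, 10, 18 move these detectable differences by 0.004 SD or less. With 20% monotone dropout at r = .70 (those weeks, normal multiplier 2.80), the slope goes from 0.375 to 0.358 and the level from 0.489 to 0.358. With a random slope of SD .02 per week (in 3-month SD units), they go from 0.364 to 0.349 and from 0.471 to 0.349. Under autoregression at .50 the level does not change (0.481).

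**The case against.** The equation is offered as an example, and the General Analytic Strategy permits other time forms and covariates. Free-intercept and constrained models are both unbiased under randomisation when the mean model is right. All of this stands: the plan does not exclude adjustment, it fails to specify it.

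A reader might take the fall from 0.469 to 0.324 SD as the general size of the loss. The documents do not support that. The fall belongs to the level contrast under compound symmetry. On the slope, at the plan's own correlation, the gain is about 5% of the detectable difference, and under autoregression the order of the two gains reverses.

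A reader might also infer large power gains for the slope test. Those would rest on assumed effect shapes and partly on misfit of the straight line. As an illustration, an effect of 0.35 SD that builds by post-treatment and then holds is fitted at r = .70 as 0.317 with free intercepts and 0.345 with the constraint. No power gain is claimed here.

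Finally, a reader might see a conflict over what is primary. The hypothesis and the Power Analysis both point to the interaction, so the Aim 2 section is loosely worded and not contradictory. The powered interaction has 4 degrees of freedom and the example's slope has 1, so carrying the label across is an interpretation, though a fair one given the statement that the power models mirror the primary tests.

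**Conclusion.** The point holds as a loss of precision and a gap in pre-specification, not as bias or an invalid test. Under the plan's common correlation of .70 the slope gains modestly and the level substantially; under other covariances the balance shifts. When the covariance is correctly specified, neither contrast loses precision: D can never be smaller than D − B²/A, and a true linear constraint cannot raise a generalised least squares variance.

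The figures assume linear time, complete data except where dropout is stated, 67 per arm and the assumed assessment weeks. Only .70 comes from the plan. The gain from the severity term cannot be quantified from the documents. The change is worth making because it is specific and needs no data; the ranking is a matter of wording alignment.

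**What to change.** For Affective Updating, BAT and PRT in the R33:

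1. Code time as 0 at pre-treatment and omit the separate treatment intercept, so that the arms share a pre-treatment mean. Dropping that term with time centred elsewhere would impose a different constraint.
2. Include the severity variable as the randomisation algorithm defines it, and name the scale.
3. Pre-specify this covariate set for these models in place of selection by association with the outcomes.
4. In the Specific Aim 2 section, repeat that the treatment by time interaction is primary, call the baseline-adjusted 3-month difference supportive, and replace the main-effect wording.

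Using the baseline score as a covariate with later visits as outcomes is an alternative for the 3-month difference only, because an interaction over the later visits leaves out change from pre-treatment. Whether time is linear or categorical is a separate choice for the sponsor, to be fixed in advance.

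The cost is analysis-plan text: no additional patients, visits or data.
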